5.2 Schedule of Events

The overall schedule of procedures and assessments is shown in [Table 1](#).

Table 1 Study AK002-003X Schedule of Assessments

Assessment Description	Prior to Dose 1	Treatment Period (25 months or longer if any monthly doses have been missed/skipped) ²⁰							Follow-Up Period (12 weeks)				
		Dose # 1 Day 1	Dose # 2 Day 29 (±3)	Doses #3–8 Day 57–197 ²⁶ (±3)	Day 211 (±3)	Doses #9–20 Day 225–533 ²⁷ (±3)	Day 547 (±3)	Doses #21–26 Day 561–701 ²⁸ (±3)	Additional Infusion Day(s) only if previous infusions have been missed ²⁹	Day 729 ¹ (±3) or 28 days after last dose	Day 736 ¹ (±3) or 35 days after last dose	Day 757 ¹ (±3) or 56 days after last dose	Day 785 ¹ (±3) or 84 days after last dose
Informed consent	X												
Prior/Concomitant Medications ²		X	X	X	X	X	X	X	X	X	X	X	X
Body weight ³		X ⁴ (predose)	X (predose)	X (predose)		X (predose)		X (predose)	X (predose)		X	X	X
Vital Signs ⁵		X ⁴	X	X		X		X	X		X	X	X
SF-36 Health Survey		X ⁴	X	X		X		X	X		X	X	X
ePRO Activation and Training ⁶	X												
ePRO Questionnaire (may include Additional Questions) ⁷		<----- Complete electronically one time daily ----->											
PGIC Questionnaire ¹³			X	X									
Baseline Diet Changes		X ⁴	X	X		X		X	X		X	X	X
Urine Dipstick Pregnancy Test ⁸		X ⁴	X	X		X		X	X		X		
Eligibility Assessment	X												
Current Safety Evaluations, as needed ⁹	X												
Access IRT to enter PID and current body weight ¹⁰		X	X	X		X		X	X				
Premedication: Prednisone ¹¹	X												
Study Drug Administration ¹²		X	X	X		X		X	X				
Symptom directed Physical Exam ¹⁴		X ⁴	X	X		X		X	X		X	X	X
Blood for Hematology with differential ^{15, 16}		X ⁴	X	X		X		X	X		X	X	X
Blood for Chemistry ^{15, 17}		X ⁴	X	X		X		X	X		X	X	X
Urinalysis ^{15, 18}		X ⁴									X		
Blood for PK ^{15, 19}		X ⁴									X		

Table 1 Study AK002-003X Schedule of Assessments

Assessment Description	Prior to Dose 1	Treatment Period (25 months or longer if any monthly doses have been missed/skipped) ²⁰								Follow-Up Period (12 weeks)			
		Dose # 1 Day 1	Dose # 2 Day 29 (± 3)	Doses #3–8 Day 57–197 ²⁶ (± 3)	Day 211 (± 3)	Doses #9–20 Day 225–533 ²⁷ (± 3)	Day 547 (± 3)	Doses #21–26 Day 561–701 ²⁸ (± 3)	Additional Infusion Day(s) only if previous infusions have been missed ²⁹	Day 729 ¹ (± 3) or 28 days after last dose	Day 736 ¹ (± 3) or 35 days after last dose	Day 757 ¹ (± 3) or 56 days after last dose	Day 785 ¹ (± 3) or 84 days after last dose
Blood for ADA ^{15, 20}		X	X	X		X ²⁰					X		
EGD with Biopsy ^{21, 22}					X		X			X			
Non-serious adverse events ²³		X	X	X	X	X	X	X	X	X	X	X	X
Adverse events of special interest ²⁴		X	X	X	X	X	X	X	X	X	X	X	X
Serious adverse events ²⁵		X	X	X	X	X	X	X	X	X	X	X	X

Table 1 Notes

ADA: Anti-Drug-Antibody

Ext: Extension

PID: Patient identification number

EGD: Esophago-Gastro-Duodenoscopy

IRT: Interactive response technology

PK: Pharmacokinetic

Eos: Eosinophil

IV: Intravenous

PRO: Electronic Patient Reported Outcome (questionnaire)

ET: Early termination

PGIC: Patient Global Impression of Change

- 1) The ET visits should be conducted 28 (± 3), 35 (± 3), 56 (± 3) and 84 (± 3) days after the last dose of study drug or prior to this, if necessary, to ensure compliance with the visit. If only one ET visit is possible, EGD and end-of-study procedures (Day 35 after last dose of study drug) may occur on the same day. If the end-of-study visit occurs more than 35 days after the last dose of study drug, then perform the visit as soon as possible. In this case, the procedures listed under the 28-day post and 35-day post study drug visit will be conducted unless otherwise directed by the Medical Monitor.
- 2) All concomitant medications taken within 30 days of enrolling into AK002-003X will be captured. All medications used during the study for the treatment of infusion related reactions, adverse events, or for the conduct of EGD will be captured.
- 3) Body weight (in kg) will be recorded on all infusion days and on follow-up Days 736, 757, and Day 785 or 35, 56, and 84 days after last dose, if ET or if previous missed infusions were made up. Current body weight, or body weight from 1 day prior will be used to calculate the amount of AK002 to be mixed with NaCl for the appropriate dose to be administered on each infusion day.
- 4) Do not collect if procedure was performed ≤ 45 days prior to Extension Day 1 (as part of the Day 113 assessment for Study AK002-003). Differential cell counts collected on Day 113 for Study AK002-003 will not be unblinded.
- 5) Vital signs including systolic and diastolic blood pressure, pulse, body temperature, and respiratory rate will be taken after the patient has been at rest for ≥ 5 minutes and before any blood draw. Vital signs will be measured on all dosing days pre-dose, 15 minutes (± 5 minutes) after the start of infusion, and immediately following the end of infusion (15 ± 5 minutes).
- 6) Activate PRO questionnaire and provide patient with unique username and password. PRO questionnaire should be activated for all patients on Extension Day 1. Patients with concomitant history of asthma, atopic dermatitis, or EoE will receive an extra question, about each, as appropriate.

Table 1 Notes cont.

- 7) The EG/EoD PRO should be completed around the same time of the day. All patients receive the 10-question EG/EoD questionnaire. Only patients with concomitant conditions of asthma, atopic dermatitis, and/or EoE will receive an additional question for each condition, as appropriate. Patients with concomitant EoE will also receive the once-daily DSQ.
- 8) Urine for Dipstick Pregnancy test will be collected predose for patients of childbearing potential on all infusion days and on Day 736 (or Day 35 after last dose of study drug, if ET or if previous missed infusions were made up). Test kits will be supplied by the central laboratory. Tests will be completed on site and evaluated prior to infusion(s).
- 9) Blood for Safety Evaluations (chemistry, hematology with differential, and urinalysis) to be collected if Extension Day 1 is >45 days from AK002-003 Day 113 or if patient was withdrawn from AK002-003 due to high eosinophil counts. Hematology and chemistry results must be available prior to randomization. If patient is suspected of exposure to helminthic parasites, stool sample should also be collected.
- 10) Cenduit IRT to be used for investigational product dispensation on all infusion days.
- 11) All patients will take 60 mg oral prednisone 12–24 hours prior to the first infusion. An approved alternative(s) may be used with the approval of the Medical Monitor. Premedication may be administered prior to subsequent infusions at the Investigator's discretion, but only with written approval from the Medical Monitor. If a patient is significantly outside their 28-day treatment window, a hematology test will be collected and the eosinophils evaluated. If the eosinophils are no longer suppressed, the patient will be given premedication of 60 mg prednisone, and the infusion may be completed using a slower infusion rate.
- 12) Study drug will be administered as a single peripheral intravenous infusion over at least 4 hours on Extension Day 1, over at least 3 hours on Extension Day 29, and over 1 to 4 hours thereafter, depending on prior tolerance to study drug infusion. Please refer to the Pharmacy Manual for detailed instructions on study drug preparation, administration, and infusion rates. Infusion must be completed within 8 hours of preparation of study drug.
- 13) Patient Global Impression of Change (PGIC) questionnaire ([Appendix 19.6](#)) will be completed by the patient on Extension Day 29 (± 3), Day 57 (± 3), and Day 85 (± 3).
- 14) A symptom-directed physical examination (including assessment of possible infusion site reactions) will be performed by the Investigator or designee, as needed, if any symptoms are reported.
- 15) Specimen processed by central laboratory. See central laboratory manual for collection and processing details.
- 16) Blood for CBC with differential, including absolute blood eosinophil and basophil counts, will be obtained just prior to each infusion and 1 hour after the end of each infusion, as well as on Extension Days 736, 757, and 785 (± 3 days) or 35, 56, and 84 (± 3 days) after last dose of study drug, if ET or if previous missed infusions were made up.
- 17) Blood for Chemistry will be obtained just prior to each infusion, as well as on Extension Days 736, 757, and 785 (± 3 days) or 35, 56, and 84 (± 3 days) after last dose of study drug, if ET or if previous missed infusions were made up.
- 18) Urine for Urinalysis will be collected on Extension Day 1 and Extension Day 736 (± 3) or 35 (± 3 days) after last dose of study drug, if ET or if previous missed infusions were made up.
- 19) Blood for PK will be collected on Extension Day 1 and Extension Day 736 (± 3) or 35 (± 3 days) after last dose of study drug, if ET or if previous missed infusions were made up.
- 20) Blood samples for ADA will be collected predose on all dosing days through Extension Day 365, on Extension Day 533 (± 3), and Extension Day 736 (± 3) or 35 (± 3) days after last dose of study drug, if ET or if previous missed infusions were made up. ADA will also be collected when an immunogenicity-related adverse event occurs.
- 21) Specimen processed by Surgical Pathologist of Dallas, via the Central Lab. See Histology Manual for processing directions.
- 22) See [Appendix 19.8](#) for biopsy assessments. EGD should occur on Day 211 (± 3), Day 547 (± 3) and Day 729 (± 3) or 28 (± 3) days after the last dose of study drug if the patient discontinues the study early or if previous missed infusions were made up, and patient agrees to have an early-termination biopsy.
- 23) Non-serious adverse events will be captured from Day 1 (first dose of study drug) through Day 785 or 84 days after last dose of study drug, if ET or if previous missed infusions were made up.

Table 1 Notes cont.

- 24) Adverse events of special interest will be captured from Day 1 (first dose of study drug) through Day 785 or 84 days after last dose of study drug, if ET or if previous missed infusions were made up.
- 25) Serious adverse events of special interest will be captured from Day 1 (first dose of study drug) through Day 785 or 84 days after last dose of study drug, if ET or if previous missed infusions were made up.
- 26) Monthly doses # 3–8 will occur on Days 57, 85, 113, 141, 169, and 197 (± 3 days).
- 27) Monthly doses # 9–20 will occur on Days 225, 253, 281, 309, 337, 365, 393, 421, 449, 477, 505, and 533 (± 3 days).
- 28) Monthly doses # 21–26 will occur on Days 561, 589, 617, 645, 673, and 701 (± 3 days).
- 29) *Only if previous infusions have been missed*, make-up dosing may occur on Day 701 + 28 days (± 3), until 26 total doses have been administered.
- 30) Doses will be considered missed if they occur more than 15 days outside the protocol-specified window.

6. Criteria for Evaluation

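### Completers who start 1 to 45 days after Day 113 have no same-day predose vital signs or CBC to compare with the checks kept at the first extension infusion

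*Combined protocol and SAP*

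**What the plan says.** Completers of AK002-003 are expected to start the extension on or about parent Day 113 (Section 5.1; Section 7.3, criterion 2). New baseline safety assessments are required only when the start is more than 45 days later, or when the patient was discontinued for high eosinophils.

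In Table 1 (Section 5.2), note 4 is attached to the Extension Day 1 cells for vital signs and hematology: "Do not collect if procedure was performed ≤ 45 days prior to Extension Day 1". Section 12.2 applies the same rule item by item. Predose vital signs and the CBC come from Day 113 unless the patient was discontinued or is past 45 days.

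The per-infusion rules in the same table state no Day 1 exception. Note 5 reads "Vital signs will be measured on all dosing days pre-dose", and Section 11.3.4 agrees. Note 16 says blood for the CBC "will be obtained just prior to each infusion and 1 hour after the end of each infusion".

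The checks after the start of the infusion are not waived. On Extension Day 1, Section 12.2 requires vital signs at 15 minutes, vital signs at the end of the infusion, and a CBC with differential 1 hour after the end.

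**The concern.** Reusing a recent visit is reasonable for confirming eligibility. It is a poor basis for a before-and-after check of a single infusion. The 15-minute and end-of-infusion vital signs and the 1-hour CBC are there to show acute change, and each needs a value taken shortly before the infusion.

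The first infusion is where this matters most. Section 2.3 reports fewer adverse events at the second and later infusions than at the first, and describes a transient lymphopenia that recovers within 24 hours. Section 13.4 lists low and high blood pressure among infusion-reaction symptoms. The next scheduled CBC after Day 1 is on Day 29, so the 1-hour sample is the only scheduled one that could show a fall of that duration. For patients who had placebo in the parent study, Extension Day 1 is also their first AK002 exposure, at 1 mg/kg; the parent active arms began at 0.3 mg/kg.

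Section 15.3 plans to summarize Extension Day 1 predose vital signs and laboratory tests, and Section 15.5 plans change from baseline. On the affected route these would rest on carried-over values, and the protocol does not say whether they will be identified as such.

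**Working it through.** The plan gives no figure to reproduce, and no power or alpha calculation applies. The check compares the rules for each entry route and counts the checks that have a comparator.

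**Inputs.** Waiver: Table 1 note 4 and Section 12.2. Per-infusion rules: notes 5 and 16 and Section 11.3.4. Checks kept on Day 1: Section 12.2. Entry routes: Sections 5.1 and 7.3. Premedication: note 11.

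**Which rule governs.** Note 4 is attached to the Day 1 cell, while notes 5 and 16 are attached to the row labels, and Section 12.2 repeats note 4. I therefore read the waiver as governing Day 1. A site that followed notes 5 and 16 would collect same-day values and could also cite the protocol.

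**Checks kept after the infusion starts.** 2 vital-sign sets (15 minutes, end of infusion) + 1 CBC (1 hour after the end) = 3.

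**Comparator by route.** Let lag = date of Extension Day 1 minus date of Day 113.

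| Entry route | Predose vital signs and CBC | Kept checks with a same-day comparator |
|---|---|---|
| Completer, lag 0 | Day 113 values, same day | 3 of 3 |
| Completer, lag 1 to 45 days | Day 113 values, 1 to 45 days old | 0 of 3 |
| Completer, lag over 45 days | Newly collected | 3 of 3 |
| Discontinued for high eosinophils | Newly collected | 3 of 3 |

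One of four routes is affected.

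**Prednisone.** Note 11 states "All patients will take 60 mg oral prednisone", taken 12 to 24 hours before the first infusion. At a lag of 2 days or more, the Day 113 CBC must precede that dose and the 1-hour CBC must follow it. At a lag of 1 day it depends on clock times. At lag 0, both samples normally follow the dose.

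**After the fix.** On the lag 1 to 45 route, checks with a same-day comparator go from 0 of 3 to 3 of 3.

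**Number of patients.** Not stated. The only bound available is planned enrollment, so 0 to about 60. The synopsis plans same-day dosing for completers, so the upper end is not a realistic estimate.

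**The case against.** The strongest reply is that the waiver is deliberate. A cell-level note is the specific exception to a row-level rule, Section 12.2 repeats it, and Section 5.1 sets the same 45-day limit. That is probably right, but it explains the choice without making a value up to 45 days old suitable as the before-infusion reading.

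Several limits stand:

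- **Timing.** This is Amendment 7, and Section 2.3 already reports the parent results by arm. Most or all first infusions on this route are probably past.
- **Analysis.** Section 15 makes no formal inference and leaves data handling to a separate statistical analysis plan, which may cover lagged values.
- **Baseline.** Blood eosinophil change is a pharmacodynamic endpoint. A count taken after prednisone should not by default replace a pre-prednisone Day 113 count.

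A reader might infer that infusion reactions would be missed. The documents do not support that. Reactions are identified by investigator judgment and symptoms within 24 hours (Section 13.4). Section 9.6 sets 4 hours of observation after the first infusion, and lymphopenia is graded on absolute counts (Appendix 19.3).

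A reader might also extend the point to other items under the waiver:

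- **Chemistry.** Note 17 says "Blood for Chemistry will be obtained just prior to each infusion", but no post-infusion chemistry is drawn, so no before-and-after comparison is lost.
- **Weight.** Note 3 ("Current body weight, or body weight from 1 day prior will be used to calculate the amount of AK002") and Sections 9.5 and 12.2 already require a current weight.
- **Pregnancy test.** Note 8 ("Urine for Dipstick Pregnancy test will be collected predose for patients of childbearing potential on all infusion days") and Sections 11.4.3 and 12.2 already require it.
- **ADA.** Section 12.2 allows the Day 113 sample, while note 20 asks for a predose sample on every dosing day through Day 365. This is a mismatch in wording.

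Nor does note 11 ("If a patient is significantly outside their 28-day treatment window, a hematology test will be collected and the eosinophils evaluated") show that a precaution is skipped. The prednisone and slower infusion it leads to already apply on Extension Day 1.

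**Conclusion.** The point holds for vital signs and the CBC, on one of four entry routes. Completers who start 1 to 45 days after Day 113 have no same-day predose comparator for any of the 3 checks kept at the first extension infusion, and the plan contradicts its own per-infusion rules there. The effect is less clear attribution of acute change at that infusion. No trial conclusion is put at risk.

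This rests on reading note 4 and Section 12.2 as governing Day 1. The first-infusion pattern in Section 2.3 applies most directly to patients who had placebo in the parent study; patients from the active arms have had AK002 before. The number affected is unknown and could be zero. This is a cheap improvement that the sponsor should make. Chemistry, weight, pregnancy test and ADA need wording alignment only.

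**What to change.** Limit note 4, for the vital signs and hematology cells, to cases where Day 113 and Extension Day 1 fall on the same day, and amend the matching Section 12.2 bullets. In all other cases take predose vital signs and a CBC on Extension Day 1. Use them as the comparator for the 15-minute, end-of-infusion and 1-hour checks. Keep the Day 113 CBC available as the pre-prednisone reference for eosinophil change from baseline, and state which value serves which summary.

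If these first infusions are already past, flag lagged Day 113 values in the Section 15.3 and 15.5 summaries, and repeat the Day 1 change-from-predose summaries without them.

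The cost is one vital-sign set and one blood draw per affected patient at a visit already taking place, plus the wording changes. The new CBC would follow prednisone, as it already does for same-day starters. If only the analysis part remains, the cost is one flag and a repeat of a few descriptive tables. The note 4 and Section 12.2 wording for chemistry, weight, pregnancy test and ADA can be aligned in the same edit.

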Test Product, Dose, and Administration	
AK002 Drug Product: 10 mL supplied in 10R Type 1 clear glass vials for IV infusion with [REDACTED] pH 6.0, in water for injection (WFI).
 
There is no placebo in this study.
 
AK002 at a dose of 1 mg/kg will be prepared according to the patient's body weight and administered via infusion pump on Extension Day 1. Starting with the second infusion (Extension Day 29), the dose of AK002 will be increased to 3 mg/kg AK002, and 3 mg/kg will be administered for infusions 2 through 26. Patients will be observed for 1 hour after the end of dosing.
 
Dosing will occur every 28 (\pm3) days for a total of 26 monthly doses. Dosing will occur on: Days 1, 29, 57, 85, 113, 141, 169, 197, 225, 253, 281, 309, 337, 365, 393, 421, 449, 477, 505, 533, 561, 589, 617, 645, 673, and 701 (\pm3 days). If a monthly infusion is delayed so that it occurs closer in the time frame to the next upcoming infusion, the late infusion will be considered skipped and may be made up after Day 701. Therefore, dosing could possibly occur on Day 729 (makeup for 1 skipped dose) and every 28 (\pm3) days after that, until 26 doses in total have been received.
 
Prior to the first infusion of AK002, 60 mg oral prednisone will be given 12-24 hours prior to the infusion. The initial IV infusion should be given over at least a 4-hour period, and the second infusion should be given over at least a 3-hour period. Subsequent IV infusions (3-26) can be given over approximately 1 to 4 hours, depending on the patient's tolerance of the previous infusions and at the Investigator's discretion. Infusion rate schedules are described in more detail in the Pharmacy Manual.

Duration of Patient Participation	
If no doses are considered skipped or missed, the total study duration for each patient will be approximately 28 months, which includes:
 
 • A treatment period of monthly AK002 infusions, administered every 28 (± 3) days in an open-label manner for a maximum of 26 intravenous doses. • A post-treatment Follow-Up Period of 84 (± 3) days following the last dose of AK002. 
If doses are considered skipped or missed, the total study duration will be extended beyond 28 months. The 84-day (± 3) post-treatment Follow-Up Period still applies after the last dose of study drug.

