9.4 Study Drug Dosage/Dosage Regimen

The first infusion of AK002 will be 1 mg/kg. Starting with the second infusion (Extension Day 29), the dose of AK002 will be increased to 3 mg/kg, and 3 mg/kg will be administered for all subsequent infusions.

Dosing will occur on Extension Days 1, 29, 57, 85, 113, 141, 169, 197, 225, 253, 281, 309, 337, 365, 393, 421, 449, 477, 505, 533, 561, 589, 617, 645, 673, and 701 (± 3 days).

If a monthly infusion is delayed so that it occurs closer in the time frame to the next upcoming infusion, the late infusion will be considered skipped and may be made up after Day 701. Therefore, dosing could possibly occur on Day 729 (makeup for 1 skipped dose) and every 28 (± 3) days after that, until 26 doses in total have been received.

The exact dose will be calculated prior to each infusion and based on current patient body weight. Study drug will be administered as a single peripheral intravenous infusion using an infusion pump as indicated in the study Pharmacy Manual at the study visits specified in [Table 1](#).

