12.3 Extension Day 29 (± 3)

The following procedures will be performed prior to study drug infusion:

- Have patient complete the SF-36 Health Survey.
- Have patient complete PGIC Questionnaire.
- Determine body weight.
- Enter PID and weight into IRT.
- Document any changes in diet from last study visit.
- Collect vital signs.
- Collect urine and perform urine pregnancy test if patient is of childbearing potential.
- Perform symptom-directed physical examination, as needed.
- Collect blood samples for CBC, blood chemistry and ADA.
- The study pharmacist will prepare study drug at 3 mg/kg using the body weight obtained at the visit. The final combined volume of the intravenous bag of study drug + 0.9% NaCl will be 120 mL.

Procedures associated with the infusion of study drug include:

- Premedication may be administered at the Investigator's discretion, in discussion with the Medical Monitor for the Day 29 infusion.
- Infuse 100 mL of study drug using an infusion pump over 3 hours on Extension Day 29. See Pharmacy Manual for Infusion Rates. Record the start and stop times of the infusion including any times the infusion is interrupted.

The following procedures will be performed after study drug infusion:

- Collect vital signs immediately following (+5 minutes) the end of infusion.
- Collect CBC with differential 1 hour (± 15 minutes) after the end of infusion.
- Observe the patient for at least 1 hour after the end of infusion.

Concomitant medication use and AE (including AESI and SAE) will be documented throughout the clinic visit.

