12.4 Extension Day 57 (± 3) to Extension Day 197 (± 3)

The following procedures will be performed on Extension Days 57, 85, 113, 141, 169, and 197 (± 3 days).

The following procedures will be performed prior to study drug infusion:

- Have patient complete the PGIC questionnaire on Extension Day 57 and Day 85 only.
- Have patient complete the SF-36 Health Survey.
- Determine body weight.
- Enter PID and weight into IRT.
- Document any changes in diet.
- Collect vital signs.
- Collect urine and perform urine pregnancy test if patient is of childbearing potential.
- Perform symptom-directed physical examination, as needed.
- Collect blood samples for CBC, blood chemistry and ADA.
- The study pharmacist will prepare study drug at 3 mg/kg using the weight obtained at the visit.

Procedures associated with the infusion of study drug include:

- Premedication may be administered at the Investigator's discretion, in discussion with the Medical Monitor for Day 57–Day 197 infusions.
- Infuse 100 mL of study drug using an infusion pump over at least 1 to 4 hours, depending on Investigator's discretion and tolerance to prior infusions. See Pharmacy Manual for Infusion Rates. Record the start and stop times of the infusion including any times the infusion is interrupted.
- Collect vital signs 15 (± 5) minutes after the start of infusion.
- An unscheduled ADA blood sample may be obtained if an immunogenicity-related AE is suspected.

The following procedures will be performed after study drug infusion:

- Collect vital signs immediately following (+5 minutes) the end of infusion.
- Collect CBC with differential 1 hour (± 15 minutes) after the end of infusion.
- Observe the patient for at least 1 hour after the end of each infusion.

Concomitant medication use and AE (including AESI and SAE) will be documented throughout the clinic visit.

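### Minimum infusion time is set by infusion number in the synopsis but by study day elsewhere, so the rules conflict (3 h or 1 h) for the second infusion if Day 29 is skipped

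*Combined protocol and SAP*

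**What the plan says.** The synopsis (Test Product, Dose, and Administration) goes by infusion number. After an initial infusion of at least 4 hours, "the second infusion should be given over at least a 3-hour period". Then: "Subsequent IV infusions (3-26) can be given over approximately 1 to 4 hours", depending on tolerance and the Investigator's judgement.

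Table 1 note 12 (Section 5.2) and Section 9.6 go by study day. Both require at least 4 hours on Extension Day 1, and then "over at least 3 hours on Extension Day 29, and over 1 to 4 hours thereafter".

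The visit lists in Section 12 are also organised by day. Section 12.3 (Day 29) reads "Infuse 100 mL of study drug using an infusion pump over 3 hours on Extension Day 29", without marking 3 hours as a minimum. Section 12.4 (Days 57 to 197) reads "Infuse 100 mL of study drug using an infusion pump over at least 1 to 4 hours".

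Section 9.4 treats the second infusion and Day 29 as one event: "Starting with the second infusion (Extension Day 29), the dose of AK002 will be increased to 3 mg/kg". The same section lets the two come apart. If an infusion is delayed until it is closer to the next one, "the late infusion will be considered skipped and may be made up after Day 701", and dosing continues "until 26 doses in total have been received". No passage exempts Day 29 from this.

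**The concern.** A limit tied to infusion number and a limit tied to study day are the same rule only while infusion 2 falls on Day 29. Once Day 29 is skipped, the second infusion given is the first 3 mg/kg dose of the extension, and it takes place at a visit whose own list allows a shorter time than the synopsis does. Two sites could treat the same situation differently, each following the protocol, and an infusion of, say, 2 hours would be a deviation under one passage and compliant under another.

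The limit bears on safety. Section 2.3 reports infusion-related reactions as the most common treatment-emergent events, two of them classified as serious, and says that most reactions arising during infusion could be handled by slowing or pausing it. Section 13.3 lists them as events of special interest.

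**Working it through.** No sample size, power or error rate is involved, and the plan states no figure to reproduce. The check is to build the dosing calendar and read off the minimum time under each rule.

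**Inputs.** Doses every 28 days from Day 1 (Section 9.4). First dose 1 mg/kg, later doses 3 mg/kg (Section 9.4). Infused volume 100 mL (Section 9.6). Minimum times as set out above.

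**Calendar.** Dose days are 1 + 28k for k = 0 to 25. The last is 1 + 28 × 25 = 701, giving 26 doses, which matches the list in Section 9.4.

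**When Day 29 counts as skipped.** Under Section 9.4 this happens once the infusion would fall nearer to Day 57 than to Day 29, that is after Day (29 + 57)/2 = 43. Table 1 note 30 uses a 15-day criterion instead. Either way a skip is possible.

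**Minimum infusion time in hours:**

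| Case | Infusion given | Nominal day | Dose | Synopsis (by number) | Note 12, Sections 9.6 and 12.4 (by day) |
|---|---|---|---|---|---|
| No skip | 1 | 1 | 1 mg/kg | 4 | 4 |
| No skip | 2 | 29 | 3 mg/kg | 3 | 3 |
| No skip | 3 | 57 | 3 mg/kg | 1 | 1 |
| Day 29 skipped | 1 | 1 | 1 mg/kg | 4 | 4 |
| Day 29 skipped | 2 | 57 | 3 mg/kg | **3** | **1** |
| Day 29 skipped | 3 | 85 | 3 mg/kg | 1 | 1 |

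Section 12.4 has no entry of its own for Days 1 and 29; those cells rest on note 12 and Section 9.6.

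**Fastest permitted mean rate** = dose / minimum time:

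- Infusion 1: 1/4 = 0.25 mg/kg/h (100/4 = 25 mL/h).
- Infusion 2, by number: 3/3 = 1.0 mg/kg/h (100/3 = 33.3 mL/h).
- Infusion 2 on Day 57, by day: 3/1 = 3.0 mg/kg/h (100/1 = 100 mL/h).

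The two rules therefore differ by a factor of 3 for that one infusion. The dose is not in doubt: Sections 9.4 and 12.4 both give 3 mg/kg. The gap since the previous infusion is 57 − 1 = 56 days instead of 28. An infusion lasting 3 to 4 hours satisfies both rules, so the conflict lies only in the lower limit.

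**The case against.** **Slot numbering.** Table 1 labels Days 57 to 197 as doses 3 to 8 and puts make-up doses in a separate column. If Day 57 is always dose 3, both rules give 1 to 4 hours there. But Section 9.4 counts doses received, so the second infusion most naturally means the second one given. If the skipped slot kept its number, the make-up after Day 701 would be the second infusion, with a 3-hour minimum in the synopsis, while Section 12.9 gives that visit 1 to 4 hours. Slot numbering moves the conflict but does not remove it.

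**Note 11.** This is a real provision for long gaps. For a patient significantly outside the treatment window it requires a hematology test. If eosinophil suppression has been lost, it requires 60 mg prednisone and permits a slower rate. It does not define how far out of window is significant, and it sets no minimum time.

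**Tolerance and discretion.** The 1 to 4 hour range depends on tolerance of earlier infusions and the Investigator's judgement, so a 1-hour infusion is permitted, not prescribed. Even so, that range allows what the synopsis does not.

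**Pharmacy Manual.** The protocol sends sites there for infusion rates, and it is not among the documents. It may settle practice, but the protocol passages would still disagree.

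**Reach.** This objection largely stands. The current text is Amendment 7. The protocol already reports the parent study's results, and entry was on or about its Day 113 or, for patients taken off treatment, within 6 months of last dosing. By inference, most patients may already be past Day 29.

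**Conclusion.** The inconsistency is real, narrow and of low severity. When Day 29 is skipped, one infusion has a minimum of 3 hours under the synopsis and 1 hour under Table 1 note 12, Section 9.6 and Section 12.4. This rests on counting infusions as given. The documents give no frequency for Day 29 skips, so the number of patients affected cannot be estimated. Section 15 plans descriptive summaries only, and no statistical result is affected.

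A reader might infer more than the documents support:

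- *That the schedule contradicts itself for everyone.* It does not; the minimum times agree when no dose is skipped.
- *That the conflict creates a 12-fold jump in rate.* The ratio 3.0/0.25 = 12 assumes the 1-hour floor, and the plan already allows that same rate at the on-schedule third infusion. What the conflict changes is the floor for one infusion.
- *That affected patients have had only a single low dose of AK002.* This fits mainly former placebo patients, about one third by the parent study's 1:1:1 allocation. Completers of the low-dose arm had four AK002 infusions, and completers of the high-dose arm had already received 3 mg/kg twice. The concern is greatest for the former placebo group.
- *That the longer early infusions are a deliberate stepped approach to the dose increase, which the conflict removes.* No visible text gives that rationale, and part of the dose rationale is redacted.

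**What to change.** Reconcile the synopsis, Table 1 note 12, Sections 9.4, 9.6, 12.3 and 12.4, and the Pharmacy Manual so that infusion-time limits use one anchor throughout, either infusion number or study day. State explicitly which limit applies to the next infusion when Day 29 is skipped, and check that Section 12.9 is consistent with the chosen anchor for make-up doses. Which limit applies is for the sponsor's clinical team to decide. In the same edit, reconcile Section 12.3, which gives 3 hours as a plain duration, with the passages that give it as a minimum.

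The cost is wording in one amendment and a matching check of the Pharmacy Manual, with no added visits or procedures. If every enrolled patient is already past the second infusion, a clarification note for classifying past deviations may be enough.
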